3.0 Background

3.1 *Summarize the relevant prior research on this topic and gaps in current knowledge within the field of study:*

Ultrasound has a rich parameter space. In addition to the fundamental frequency, parameters include intensity (directly relates to pressure), duration, number of cycles (relates to pulse duration), duty cycle and pulse repetition frequency (PRF). There are multiple studies in small and one in large animals explicitly testing how different parameters affect neuromodulation. King et al. (in mice) found that the product of intensity and duration best predicted success rates, Kim et al. (in rats) found a strong inter-dependency on duration and duty-cycle such that 300 milliseconds of LIFU at 50% duty cycle was most effective, and Yoo et al. (in rabbits) found PRF interacted with duty cycle such that high duty cycles (50%) at low PRFs (10 Hz) resulted in excitation whereas higher PRFs (100 Hz) at low duty cycle (5%) resulted in inhibition. In large animal (sheep), Yoon et al. reported inhibition was best achieved with a 3 and 5% duty cycle at PRFs of 60 and 100 Hz respectively and that 0.5 milliseconds at 70% duty cycle to be most effective for excitation. There are now several studies in primate and human showing neuromodulatory effect, though parameters have not been explicitly been tested.

Additionally, we have conducted a retrospective study of symptoms and safety in TMS and LIFU, which reported no serious adverse events in any of the studies monitored (Sci Rep 2020 [name]).

3.2 *Describe any relevant preliminary data:*

Primary motor cortex. We have collected $N = 6$ healthy participants under a full-parametric design looking at 3 intensities (6 W/cm², 12 W/cm², 24 W/cm² Isppa in the head), 6 duty cycles (1%, 5%, 10%, 30%, 50%, 70%), 3 durations (100 msec, 500 msec, 1000 msec) and 4 PRFs (10 Hz, 100 Hz, 500 Hz, 1000 Hz) delivered to the primary motor cortex using concurrent and concentric TMS/LIFU (Sci Rep 2018 [name]).

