Stereotaxic Neuronavigation: Stereotaxic neuronavigation is the process of using a subject-specific anatomical MRI/CT images and co-registering them to their actual head and the LIFU transducer and TMS coil for real-time navigation of the treatment. The subject is fitted with a head-band that contains 3D infrared tracking bulbs. The LIFU transducer is also fitted with these tracking bulbs. Both the subject and treatment device are then tracked in real-time using an infrared camera. This procedure allows for precise targeting of specific brain regions using the subject-specific MRI and is wholly noninvasive. This procedure is ongoing throughout the experiment during the LIFU and TMS intervention.

- 7.2 List the name of all drugs (including any vitamins, supplements, herbs, or nicotine) to be used in the study. Indicate whether they have FDA approval, and list any limitations for their use:*

N/A

- 7.3 List all devices, how they will be used, their purpose in the study, and if they will be used in a manner consistent with their approved uses. If they will be used in ways that are not yet FDA approved, indicate whether they need an IDE or a determination that they are exempt from the IDE Determination. If a determination of significant risk or non-significant risk is needed for any of the devices, include the researcher's recommendation for each of those devices:*

LIFU: In its current state, ultrasound for neuromodulation follows the safety guidelines of the Food and Drug Administration (FDA) for obstetric diagnostic ultrasound and adult cephalic applications. The device is not FDA approved for neuromodulation. . The device has been deemed a nonsignificant risk (NSR) by the FDA. These include derated limits of spatial peak pulse average (Isppa) of 190 W/cm², a spatial peak temporal average of 720 mW/cm² (94 mW/cm² for adult cephalic) and a mechanical index (MI = peak negative pressure/ \sqrt{fc}) of 1.9. MI is an indication of the ability to produce cavitation related bio-effects and can be used as an indication for potential micromechanical damage. We will use less than 50 W/cm² (4x lower Isppa) for these studies.

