In addition to settings listed above, the following parameters are to be tested in this study. 3 Intensity (I) settings (6, 12, and 24 W/cm²), 6 duty cycle (DC) settings ranging from 1-70%, 3 duration (Dur) settings ranging from 100ms-1s, and 4 pulse repetition frequency (PRF) settings ranging from 10-1000Hz. As this is a parametric design, we are testing 216 ultrasound settings. Though each setting will take less than 1 minute to test, testing is

expected to be divided between 6 study sessions (up to 36 per session) to reduce burden to the participant.

These levels of energy are adhered to in human ultrasonic neuromodulation studies though there are no specific guidelines for energy deposition for ultrasonic neuromodulation and indeed, explicit expository and dosimetry for diagnostic and therapeutic applications, despite their prevalence and long history, has proven challenging and is still largely lacking. Ultrasound for transient neuromodulation is different from the use of ultrasound for surgery where very high intensities are used to thermally ablate tissues or for blood-brain barrier (BBB) opening where high intensities are also used in combination with contrast agents to intentionally produce cavitation as a means of opening the BBB. To date, a total of $N = 179$ in 8 published studies of healthy neurologically intact participants (plus one 1 TBI patient) have undergone a variant of LIFU for neuromodulation with no published report of severe adverse events. We have published on minor adverse events from LIFU ([name] et al. 2020).

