LIFU: Low-intensity focused ultrasound (LIFU) is a method of brain neuromodulation using ultrasonic acoustic energy. An ultrasound transducer is placed on the participant's head and is tracked using the neuronavigation system. Brief ultrasound pulses are delivered to the desired brain area. A small amount of ultrasound gel will be placed on the face of the single-element focused ultrasound transducer. The transducer will then be fitted on the scalp over the desired brain area and held in place with a mechanical arm. Brief pulses (0.1-1.0 seconds; duty cycle 1 – 70%; pulse repetition frequency 10 – 1000 Hz) of low-intensity (< 50 W/cm² Isppa), sub-thermal ultrasound (0.3 - 0.5 MHz) will be delivered in order to determine the area of activation, as well as the patterns of brain activity generated. Subjects may experience a mild buzzing sensation on their scalp depending upon stimulation parameters used. Participants will be familiarized with the sensations before formal testing. The ultrasound intensity used will be below the intensities recommended for the safe use of ultrasound by the FDA (190 W/cm² Isppa) and will be brief in duration at these low-intensities as not to generate any heating. While no discomfort is anticipated, participants will be informed if they experience any warming sensation on their scalp or discomfort to notify the investigator and the procedure will be immediately terminated. Participants may be given ear plugs to wear during the procedure and/or a white noise machine may be utilized in the testing space. This is to provide ear protection and noise cancellation to reduce participant focus on LIFU device function. We have significant experience using LIFU including our published reports of human neuromodulation experiments.

TMS: transcranial magnetic stimulation (TMS) is a noninvasive method of stimulating the brain using magnetically induced electrical currents. The stimulating coil is placed over a subject's motor cortex and a single pulse is conducted. This is repeated 10-20 times at an inter-stimulus interval of 5-10 seconds per trial. A threshold setting will be determined for each participant before each study session to obtain an average motor evoked potential of approximately 0.75mV, measured with EMG recordings. This will be the setting used throughout the testing session.

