All individuals who will be operating the scanners are required to pass an fMRI safety training course. However, it should be noted that over the past several years and over 3000 imaging sessions, we have had no scanner-related emergencies.

CT Data Collection: Participants will undergo a head CT to obtain necessary images of their skull. CT scans will be a low-dose scan with expected radiation dose of about 2mSv. This does give a lifetime cancer risk of about 1 in 10,000. The lifetime natural incidence rate is about 1 in 2. Equipment will be operated by trained personnel only.

To reduce both time burden and ionizing radiation exposure, if previous MRI or CT scans have been taken with the [name] lab, they can be used in this study and the first study visit procedures may be omitted.

Low-Intensity Focused Ultrasound: Brief pulses (0.1-1.0 seconds; duty cycle 1 – 70%; pulse repetition frequency 10 – 1000 Hz) of low-intensity (< 50 W/cm² Isppa), sub-thermal ultrasound (0.3 - 0.5 MHz) will be delivered in order to determine the area of activation, as well as the patterns of brain activity generated. Subjects may experience a mild buzzing sensation on their scalp depending upon stimulation parameters used. Participants will be familiarized with the sensations before formal testing. The ultrasound intensity used will be below the intensities recommended for the safe use of ultrasound by the FDA (190 W/cm² Isppa) and will be brief in duration at these low-intensities as not to generate any heating. While no discomfort is anticipated, participants will be informed if they experience any warming sensation on their scalp or discomfort to notify the investigator and the procedure will be immediately terminated.

Comparison between the LIFU parameters used in proposed study to those for obstetric diagnostic imaging: The FDA guidelines for obstetric diagnostic images include derated limits of spatial peak pulse average (Isppa) of 190 W/cm², a spatial peak temporal average of 720 mW/cm² and a mechanical index (MI = peak negative pressure/ \sqrt{fc}) of 1.9. This study will use less than 50 W/cm² (4x lower Isppa) for these studies. We have significant experience using LIFU including our published reports of human neuromodulation experiments.

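### Protocol 7.3 and 17.1 imply compliance with FDA time-average limits that are never computed; on stated assumptions the top settings exceed 94 mW/cm² and, averaged per stimulus interval, 720 mW/cm²

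*Protocol*

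**What the plan says.** Protocol 7.3 opens its account of the device by saying that "ultrasound for neuromodulation follows the safety guidelines of the Food and Drug Administration (FDA) for obstetric diagnostic ultrasound and adult cephalic applications". It then lists three derated limits: Isppa 190 W/cm², "a spatial peak temporal average of 720 mW/cm² (94 mW/cm² for adult cephalic", and a mechanical index of 1.9. The study's own exposure is compared with the first of these only: "We will use less than 50 W/cm² (4x lower Isppa) for these studies". The same section notes that the FDA deemed the device nonsignificant risk.

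The settings follow: "3 Intensity (I) settings (6, 12, and 24 W/cm²), 6 duty cycle (DC) settings ranging from 1-70%, 3 duration (Dur) settings ranging from 100ms-1s", and four pulse repetition frequencies, 216 combinations in all. Protocol 3.2 lists the pilot grid with the same three intensity levels, labelled "3 intensities (6 W/cm², 12 W/cm², 24 W/cm² Isppa in the head".

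Protocol 17.1 sets this study's parameters against the obstetric diagnostic limits. It repeats "a spatial peak temporal average of 720 mW/cm² and a mechanical index" but leaves out the adult cephalic value, and again gives only the Isppa comparison. On timing, Protocol 8.2 says of the TMS pulse: "This is repeated 10-20 times at an inter-stimulus interval of 5-10 seconds per trial".

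The SAP (2.1 to 2.3) reduces the grid to 20 combinations: 6 and 24 W/cm²; 1, 10, 30, 50 and 70% duty cycle; 100 and 500 ms. Ultrasound is given concurrently with TMS, with 20 stimulations per trial. Neither document calculates an Ispta for any setting.

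**The concern.** Isppa describes intensity while a pulse is on. It is the same at 1% and at 70% duty cycle, and the same for a 100 ms and a 1 s train. Duty cycle and duration are factors of the experiment, so the Isppa margin says nothing about how exposure varies along those two axes. Ispta does vary with them, and it is the cited limit that goes unchecked.

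What is at stake is the accuracy of an exposure statement that readers of 7.3 and 17.1 rely on. If the highest settings exceed a value listed in the same sentence as the one they satisfy, the text credits the study with a safety property those settings do not have. The omission in 17.1 adds to this: the participants are adults receiving ultrasound to the head, and the value dropped is the one for adult cephalic use.

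**Working it through.** **The plan's own figure.** 190 / 50 = 3.8, which rounds to the stated factor of 4. At the highest level actually tested, 190 / 24 = 7.9. The Isppa statement is correct. The grid size also reproduces: 3 × 6 × 3 × 4 = 216 = 6 sessions × 36.

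**Inputs.**
- Intensity: 6, 12, 24 W/cm² (Protocol 7.3); 6, 24 (SAP 2.1).
- Duty cycle: 1, 5, 10, 30, 50, 70% (range in 7.3, levels taken from the pilot list in 3.2); 1, 10, 30, 50, 70% (SAP 2.1).
- Duration: 0.1, 0.5, 1 s (range in 7.3, levels from 3.2); 0.1, 0.5 s (SAP 2.1).
- Interval: 5–10 s (Protocol 8.2). The SAP gives none, so the Protocol's is used.

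**Assumptions.** The intensity levels are in the head; there is one ultrasound train per TMS pulse; averaging is over one stimulus interval.

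**Formula.** Ispta (mW/cm²) = 1000 × Isppa × duty cycle × duration / interval. Pulse repetition frequency does not enter.

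**Top settings.**
- Protocol (24 W/cm², 70%, 1 s): 24 × 0.70 × 1.0 = 16.8 J/cm² per train. 16.8 / 5 gives 3,360 mW/cm²; 16.8 / 10 gives 1,680.
- SAP (24 W/cm², 70%, 500 ms): 24 × 0.70 × 0.5 = 8.4 J/cm² per train. 8.4 / 5 gives 1,680 mW/cm²; 8.4 / 10 gives 840.

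Against 720 these are ratios of 4.7 and 2.3 (Protocol), and 2.3 and 1.2 (SAP). Against 94 they are 35.7 and 17.9, and 17.9 and 8.9.

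**Counts over the grids.** The Protocol has 54 intensity × duty cycle × duration cells, each at four pulse repetition frequencies.

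| | Above 720, 5 s | Above 720, 10 s | Above 94, 5 s | Above 94, 10 s |
|---|---|---|---|---|
| Protocol cells (of 54) | 9 | 4 | 31 | 23 |
| Protocol settings (of 216) | 36 | 16 | 124 | 92 |
| SAP settings (of 20) | 2 | 1 | 10 | 8 |

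At 5 s one further SAP setting (24 W/cm², 30%, 500 ms) sits exactly at 720 and is not counted.

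**Sensitivity to the averaging window.** The documents give no window.
- Over one setting's share of a session, 2.5 h / 36 = 9,000 / 36 = 250 s. The SAP top setting is 8.4 × 10 / 250 = 336 to 8.4 × 20 / 250 = 672 mW/cm². The Protocol top setting is 16.8 × 10 / 250 = 672 to 16.8 × 20 / 250 = 1,344.
- Over a whole session of 36 randomly chosen Protocol settings, the mean energy per train is 14 × 0.2767 × 0.5333 = 2.066 J/cm². Then 2.066 × 36 × 10 / 9,000 gives 83 mW/cm², and 20 repetitions give 165.

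**Sensitivity to the intensity scale.** If 24 W/cm² were device output, skull transmission would scale the result; the documents give no figure for it. Averaged per interval, the SAP top setting would fall to 720 at transmission 720 / 1,680 = 0.43 (5 s) or 720 / 840 = 0.86 (10 s). It would fall to 94 only at 0.056 or 0.112. For the Protocol top setting the corresponding values are 0.21 or 0.43, and 0.028 or 0.056.

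**The case against.** **The wording describes the field.** The opening sentence of 7.3 is about ultrasound for neuromodulation in general. So is "These levels of energy are adhered to in human ultrasonic neuromodulation studies", which goes on to say that no guideline specific to neuromodulation exists. A reader might infer from that second sentence that the study commits itself to the FDA limits. It does not: it can equally refer to the study's own settings, and it carries its own disclaimer. The only numerical cap set for this study is 50 W/cm² Isppa, and the grid meets it. This part of the objection stands. The implication of compliance nevertheless remains, because 17.1 compares this study's own parameters with the listed limits.

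**The figures rest on assumptions.** SAP 2.2 says only that delivery is concurrent with TMS, the 5–10 s interval is given for TMS, and the in-head label comes from the pilot. This stands. The assumptions are the natural reading: Protocol 8.2 describes CT-based modelling to obtain accurate intensities inside each participant's skull. They should still be stated in the plan.

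**The averaging window decides the 720 result.** This also stands. Over 250 s per setting the SAP top setting is below 720, and the session mean is well below it. The 94 value behaves differently: the top settings exceed it over the stimulus interval and over 250 s.

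**Safety is addressed by other means.** There is the nonsignificant-risk determination, a rationale that the effect is mechanical and not thermal, and a rule to stop on any sensation of warming. A reader might infer from the ratios that the settings are unsafe. The documents do not support that.

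**Consequences for the analysis.** A reader might also infer that the high-duty-cycle cells would have to be dropped, leaving the SAP 4.3 ANOVA incomplete. Nothing in the documents proposes dropping cells. In the SAP grid only one of the four 70% settings exceeds 720, so the hypothesis about duty cycles above 50% stays testable.

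**Conclusion.** The exposure statement in Protocol 7.3 and 17.1 needs correcting. It cites a time-average limit, never computes the time average, and supports itself with a quantity that cannot respond to two of the factors being varied.

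With in-head levels, one train per TMS pulse and averaging over 5–10 s, the top settings are 1.2 to 4.7 times the 720 mW/cm² value and 8.9 to 35.7 times the adult cephalic value. Exceeding 94 is the firmer result: on the in-head scale the top settings do so on both per-setting windows examined, and about half of the SAP settings do so per stimulus interval. Exceeding 720 is conditional on the averaging window. The finding concerns a limit that is cited but not checked. It gives no evidence of harm and does not invalidate the SAP's factorial analysis.

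**What to change.** In Protocol 7.3 and 17.1:

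1. State whether 6, 12 and 24 W/cm², and the 50 W/cm² cap, are in-head or device-output Isppa.
2. Add a table of Ispta for each intensity × duty cycle × duration cell (54 for the Protocol grid, 20 for the SAP grid), giving the stimulus interval and the averaging window used.
3. Add the 94 mW/cm² adult cephalic value to 17.1.
4. Replace the implied compliance with a statement of which cited Ispta values are exceeded and by how much, and that the study relies on the nonsignificant-risk determination for those settings.

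The cost is one table and a few sentences; the grid, the stimulation schedule and the analysis are unchanged. The downside is that the stated safety margin becomes less favourable. Lengthening the stimulus interval is not a substitute: even at 12 s the SAP top setting would be 8.4 / 12 = 700 mW/cm², still 7.4 times the adult cephalic value, and 12 s lies outside the Protocol's 5–10 s range.

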8.0 Procedures Involved

- 8.1 *Describe and explain the study design:*

This is a systematic study of set parameters in a multiple visit study.

Session 1: MRI and CT anatomical scans

Session 2-7: LIFU parameter testing with TMS and EMG while utilizing neuronavigation and physiological data collection such as PPG, BP, ECG, Respiration, and/or GSR.

- 8.2 *Provide a description of:*

- *All research procedures being performed*
- *If the study has more than one procedure, session, and/or subject population, describe each procedure, session, and/or study population separately. For complex studies, you are encouraged to include a figure or chart.*

Recruitment and Screening: Individuals indicating interest in participating in this research study will complete a screening and demographic form as part of the screening process (see Safety Screening Form and Demographic Form). This information will be reviewed to determine eligibility and to screen for any contraindications to MRI, CT, and TMS.

Consent: Participants will be asked to sign a consent form upon arrival for their first study visit. Participants will have as much time as they need to review the consent form and may ask questions of the PI or study team prior to participation.

Pregnancy Screening: Prior to any study procedures, female participants will provide a urine sample which will be screened for pregnancy. As indicated in the consent form, if

testing indicates the participant is pregnant, they will be notified and excluded from the study.

Participants will be healthy adults age 18-65 with no contraindications to MRI, CT, or TMS. We will enroll approximately 80 individuals.

This study includes low-intensity focused ultrasound (LIFU), transcranial magnetic stimulation (TMS), magnetic resonance imaging (MRI), and computed tomography (CT). Additionally, stereotaxic neuronavigation is utilized.

Study Procedures:

Session 1	Session 2-7
Imaging	36 Parameter Trials
MRI & CT	LIFU + TMS
2.5 hours	2.5 hours

*parameters per session will be chosen randomly within the set values

Session 1 - An MRI and CT exam will be performed and questionnaires will be administered.

Sessions 2-7 - Utilizing imaging collected on previous visit, subjects will complete a testing session. These sessions will involve LIFU and TMS stimulation. Additionally EMG, PPG, BP, ECG, Respiration, and GSR will be collected. Questionnaires will be administered at each session.

Follow up - An electronic questionnaire of Report of Symptoms will be sent about 1 week following final study participation. If requested, this questionnaire can be completed verbally on the phone with study staff.

MRI session: Participants will receive an MRI scan to obtain a high-resolution image of their head to be used for proper setup of LIFU parameter sessions. During the MRI session, the experimenter and participant are able to communicate with one another at all times, ensuring the comfort of the subject. In addition, participants are provided with an emergency 'squeeze bulb' which can terminate the scanning procedure at any time.

CT session: Participants will receive a CT scan to obtain detailed imaging of the skull. CTs are collected as this is the only current option to properly image the skull. This is necessary for our computer models of acoustic wave propagation to ensure accurate intracranial intensities for each individual.

Stereotaxic neuronavigation: Stereotaxic neuronavigation allows us to track the positioning of the ultrasound transducer on the subject's head in real time using the MR/CT images for guidance.

LIFU: Low-intensity focused ultrasound (LIFU) is a method of brain neuromodulation using ultrasonic acoustic energy. An ultrasound transducer is placed on the participant's head and is tracked using the neuronavigation system. Brief ultrasound pulses are delivered to the desired brain area. A small amount of ultrasound gel will be placed on the face of the single-element focused ultrasound transducer. The transducer will then be fitted on the scalp over the desired brain area and held in place with a mechanical arm. Brief pulses (0.1-1.0 seconds; duty cycle 1 – 70%; pulse repetition frequency 10 – 1000 Hz) of low-intensity (< 50 W/cm² Isppa), sub-thermal ultrasound (0.3 - 0.5 MHz) will be delivered in order to determine the area of activation, as well as the patterns of brain activity generated. Subjects may experience a mild buzzing sensation on their scalp depending upon stimulation parameters used. Participants will be familiarized with the sensations before formal testing. The ultrasound intensity used will be below the intensities recommended for the safe use of ultrasound by the FDA (190 W/cm² Isppa) and will be brief in duration at these low-intensities as not to generate any heating. While no discomfort is anticipated, participants will be informed if they experience any warming sensation on their scalp or discomfort to notify the investigator and the procedure will be immediately terminated. Participants may be given ear plugs to wear during the procedure and/or a white noise machine may be utilized in the testing space. This is to provide ear protection and noise cancellation to reduce participant focus on LIFU device function. We have significant experience using LIFU including our published reports of human neuromodulation experiments.

TMS: transcranial magnetic stimulation (TMS) is a noninvasive method of stimulating the brain using magnetically induced electrical currents. The stimulating coil is placed over a subject's motor cortex and a single pulse is conducted. This is repeated 10-20 times at an inter-stimulus interval of 5-10 seconds per trial. A threshold setting will be determined for each participant before each study session to obtain an average motor evoked potential of approximately 0.75mV, measured with EMG recordings. This will be the setting used throughout the testing session.

EMG: Electromyography (EMG) involves attaching disposable surface electrodes to the skin overlying muscles of interest of the hand and forearm in order to record muscular activity. Identification of the muscle is achieved by asking the participant to hold a light tonic contraction. The skin may be prepared with a mild abrasive gel to remove dead skin and surface debris and subsequently disinfected with rubbing alcohol. EMG electrodes are held in place with double sided tape. This signal is used to detect LIFU effects and TMS amplitude.

PPG, GSR, ECG, BP, Respiration: Photoplethysmograph (PPG) and galvanic skin response (GSR) will be collected using a lightweight wearable Shimmer3 GSR+ unit and blood pressure will be collected using a wireless blood pressure monitor (QardioArm). A commercial respiration belt (SleepSense) will be wrapped around the chest to collect continuous respiration data. Electrocardiogram (ECG) will be collected using two leads. This data is collected to assess for any effects of ultrasound but more importantly as a monitor of the state of the participants' autonomic nervous system as a potential contributor/confound that may affect responses.

Questionnaires: Questionnaires will be collected either electronically using a VT approved platform such as Redcap, or on paper. The following questionnaires will generally be completed during the imaging and consent visit but may be completed at following visits if time does not allow during the first visit: Beck Depression Inventory-II (BDI), Beck Anxiety Inventory (BAI), State Trait Anxiety Inventory (STAI), International Physical Activity Questionnaire (IPAQ), Medical Outcomes Survey Short Form-8 (SF-8), Sleep Scale from the Medical Outcomes Study, Patient Health Questionnaire-2 (PHQ-2), Generalized Anxiety Disorder 2-item (GAD-2), Tobacco, Alcohol, Prescription medications, and other Substance Tool (TAPS), and Perceived Stress Scale (PSS). Questionnaires may be used as a means of documenting potential confounds such as anxiety, fear, depression, etc. Questionnaires are estimated to take 30-45 minutes to complete. Additionally, the STAI (state only), Experience Questionnaire, Daily Questionnaire, and Report of Symptoms questionnaires will be administered at all stimulation sessions (sessions 2-7). The Daily Questionnaire exists to help quantify any variance between participant sessions. This includes items such as amount of sleep, hormone changes, and caffeine intake. Lastly, subjects will be contacted up to one month following the final session to complete the participant Report of Symptoms questionnaire. All questionnaires are attached to this application.

8.3 *Describe:*

- *Procedures or safeguards intended to reduce the probability and magnitude of risks. (For example: Reducing the risk of injury in a virtual reality study either by having the subjects sit during the study or by providing an obstacle-free space for walking.)*
- *Be sure to describe all drugs and devices used in the research, when they will be administered or used, and their purpose.*
- *Methods used to collect data about subjects. Please upload all data collection forms to Protocol Management. Some common examples are:*
 - *Screening questionnaires*
 - *Survey(s), including online surveys*
 - *Demographic questionnaire(s)*
 - *Interview guide(s), e.g., questions or pool of questions for semi-structured interviews*
 - *Focus group guide(s)*
 - *Other documents used to collect data*

Every effort will be made to ensure the subject's comfort and to reduce any risk. Subjects will be thoroughly screened to ensure that MR and CT contraindications are not present. All females will be screened for pregnancy. If, at any time, subjects experience discomfort, dizziness, or claustrophobia they will be able to discontinue immediately.

During MRI scanning subjects will have access to an emergency squeeze bulb they can indicate at any time. Staff operating the MRI undergo Advanced MR/Operator Training. This is required for persons wishing to conduct research on the Human Neuroimaging Lab (HNL) MRIs. Training consists of presentations, observation, and hands-on practice. Topics include safety and emergency procedures, subject screening and preparation, scanner set-up and operation, and troubleshooting. Each person must also complete at least 4 hours of observation (to include 2 different studies) and at least 16 hours of supervised scanning (to include 4 different studies). Certification is granted upon completion of the training and passing of a competency exam.

During CT scanning subjects will be in communication with the trained technician. A trained and certified radiology technician will operate the CT.

During LIFU stimulation sessions participants will be in constant communication with the study staff. Staff operating the LIFU device, TMS device, and EMG/PPG/BP/GSR/ECG/Respiratory recording device will undergo training under the direction of the PI. Additionally, participants will be reminded they can terminate the session at any time. Screening for side effects will take place pre and post all stimulation sessions.

Methods used to collect data:

We will collect questionnaires and screening information (see attached forms and questionnaires) using an electronic Virginia Tech approved system such as Redcap or Qualtrics, or via paper form.

The MRI and CT will be used to collect brain images, and EMG will be used to collect muscle contraction signals. Standard devices will be used to collect PPG, BP, ECG, Respiration, and GSR data. All data will be stored on FBRI servers with the subject coded identifier.

*8.4 What data will you collect during the study and how you will obtain them?
Please include descriptions of electronic data collection, database
matching, and app-based data collection:*

Images will be obtained of the subjects' head/brain from MRI and CT scans. EMG signals will be collected using standard EMG equipment. Photoplethysmograph (PPG), blood pressure, heart rate, respiration, and galvanic skin response data will be collected using standard equipment. Electronic data such as questionnaires or screening forms may be collected through secure web-based survey tools, such as RedCap, provided by Virginia Tech. The Daily Questionnaire exists to help quantify any variance between participant sessions. This includes items such as amount of sleep, hormone changes, and caffeine intake. Additionally, questionnaire or screening data may be recorded on paper, entered into a digital database and then stored securely. All data will be stored on secure FBRI servers.

8.5 *Who will transcribe or code audio and/or video recordings?:*

N/A

8.6 *Include a description of any deception to be used in the study. Include justification for the use of deception (why the deception is necessary), describe the debriefing process, and describe how the study meets all the following criteria for alteration of consent (deception is considered an alteration of informed consent):*

- *The research involves no more than minimal risk to the subjects*
- *The alteration will not adversely affect the rights and welfare of the subjects*
- *The research could not practicably be carried out without the alteration/deception*
- *(Optional but encouraged in most cases) Subjects will be provided with additional pertinent information after participation (i.e., debriefing for studies involving deception)*

N/A

8.7 *If the study involves long-term follow-up (once all research related procedures are complete), describe what data will be collected during the follow up period and when it will occur:*

N/A

